5.4. Derived Variables

Baseline Value

The last non-missing value prior to first dose of study drug. If a subject does not receive any study drug, baseline is the latest recorded measurement on or before the randomization date.

Change from Baseline Value

Change from baseline value is the arithmetic difference between a value of interest and a baseline value: Change from baseline value = (value of interest – baseline value).

Percent Change from Baseline Value

The ratio of the arithmetic difference between a value of interest and the baseline value to the baseline value multiplied by 100: (Change from Baseline / Baseline) \times 100.

Time to Complete Wound Closure

Time to complete wound closure is the time interval (in days) from Day 0 to the date of the first visit date within the allowed visit window where wound closure is so indicated by the investigator. If a subject has not experienced complete wound closure, the subject will be considered censored at the subject's end of study date.

Time to a major amputation in the target limb

Time to a major amputation in the target limb is the time interval (in days) from Day 0 to the earliest date of a reported AE of an amputation of the lower extremity above the ankle of the target limb.

Time to a minor amputation in the target limb

Time to a minor amputation in the target limb is the time interval (in days) from Day 0 to the earliest date of a reported AE of an amputation of a foot or any parts of a foot such as toes on the target limb.

Absolute Differentials

If not provided by the individual study center labs, values for the absolute differentials (i.e., neutrophils, lymphocytes, monocytes, eosinophils, and basophils) will be calculated by multiplying the WBC count by the corresponding percent differential in the total WBC count. Results should be rounded to the nearest hundred for units equivalent to $10^3/\mu L$.

Percent Differentials

If not provided by the individual study center labs, values for the percent differential (i.e., neutrophils, lymphocytes, monocytes, eosinophils, and basophils) will be calculated by dividing the corresponding absolute differential count by the total WBC count. Results should be rounded to the tenth of a percentage point.

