3.5.2. DISCONTINUED SUBJECTS

Any subject may voluntarily discontinue the study at any time without prejudice. The investigator may discontinue a subject from the study at any time if (s)he considers that remaining in the study compromises the subject's health or the subject is not sufficiently cooperative. In either event, reason(s) for discontinuation should be recorded on the study worksheets.

Possible reasons for study discontinuation include the following:

- Adverse events necessitating discontinuation from the study.
- The subject is lost to follow-up.
- Subject decision (specify).
- Investigator decision (specify).
- Other reason (specify).

The reasons for any subject discontinuation will be recorded on the study completion form of the study worksheets.

Additional subjects may be enrolled if subjects discontinue prior to the 4 Month visit in order to achieve a 300-subject dataset with 4-month data.

Subjects discontinued for AE(s) will be followed-up after subject's discontinuation until the event is resolved or considered medically stable by the investigator.

Subjects that withdraw after receiving any treatment injections but prior to study completion will undergo the following, if possible:

- Vital signs
- Concomitant medications
- Documentation of the target ulcer (photograph and measurements of surface area, depth, perimeter and volume) before and after debridement.
- Serum chemistry and hematology
- Serum HGF if discontinued prior to Day 90
- Copies of VM202 in whole blood if discontinued prior to Day 90
- Injection site reaction assessment if discontinued prior to Day 60
- Adverse event assessment

In case of a subject lost-to-follow-up, the investigator/designee must do his/her best to contact the subject (by phone or letter) at least twice. If no response is obtained from the subject, the investigator is encouraged to contact one of the subject's

relatives or his/her general practitioner. Documentation of these contacts must be recorded in the subject medical chart. It can be, for instance, the acknowledgement of receipt of a letter sent to the subject.

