3. STUDY DESIGN

This is a phase III, randomized, double-blind, placebo-controlled, multicenter, 7-month study designed to assess the safety and efficacy of intramuscular injections of VM202 in the calf of diabetic patients with chronic nonhealing foot ulcers and concomitant PAD. Subjects with confirmed PAD and diabetes aged \geq 18 years to \leq 80 years diagnosed with nonhealing foot ulcers will be screened for study eligibility after giving informed consent.

At Screening, standard of care will be initiated that will continue for the duration of the study, as follows:

- Surgical debridement of necrotic tissue or devitalized tissue
- Use of appropriate off-loading when ambulating
- Maintenance of moist wound environment

Three hundred patients (from up to 30 study centers) who meet the eligibility criteria will be randomized in a 2:1 ratio to one of two treatment groups: 200 patients with VM202 (16 mg) plus standard of care or 100 subjects with placebo plus standard of care, respectively. Safety will be monitored throughout the study by an independent Data Safety Monitoring Board (DSMB, Section 8.5).

Patients will receive intramuscular injections in the ipsilateral calf of the affected foot with the target ulcer of either VM202 or placebo on Day 0, Day 14, Day 28, and Day 42 as follows:

Treatment: Days 0, 14, 28, and 42

TREATMENT]	DOSE VM20	FINAL DOSE		
GROUP	DAY 0	DAY 14	DAY 28	DAY 42	VM202 (mg)
VM202	4	4	4	4	16
Placebo	0	0	0	0	0

0 indicates injections of Placebo

VM202 will be delivered in a solution of 0.5 mg VM202 / mL. All subjects will receive sixteen (16) 0.5-mL intramuscular injections of VM202 or placebo at each injection visit.

The schedule of study visits and the clinical parameters that will be measured at the visits are summarized in Table 1 to Table 3 below.

The subjects' target ulcer will be evaluated by photograph, surface area, depth, perimeter and volume measurements. Subjects must have a non-healing ulcer on Day 0 that meets study entry inclusion criterion # 5 and does not meet exclusion criterion #6 to be eligible for study participation. Subjects will continue to come to the clinic once a week for dressing changes and wound assessment until the ulcer has healed or study exit, whichever comes first. Measurement of the target ulcer will be performed at each follow-up visit until complete wound closure or study exit.

Further details on the study procedures and conduct are provided in the protocol.

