8.4. Multiplicity Adjustment

No multiplicity adjustment will be performed since the study has one primary efficacy endpoint with one primary population and analysis method. Sensitivity analyses for the primary efficacy endpoint are supportive and analyses for other efficacy endpoints are exploratory.

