8.6.3. Missing Dates and Times

If a start or stop date for an adverse event or a concomitant medication is completely missing, it will not be imputed. If that date is partially missing, imputed dates specified in Table 6 will be used to derive the duration of the adverse event or the duration of the medication use. If the start or stop date for an adverse event is not missing but the corresponding time is partially or completely missing, imputed times specified in Table 7 will be used to derive the duration of the adverse event. For adverse event attribution relative to a specific injection, a missing start date and time should default to the date and time of the immediately documented prior injection. Missing years will not be estimated under any conditions.

Table 6 Imputation Rules for Partial Adverse Event or Concomitant Medication Start and Stop Dates

	Missing	IMPUTATION	EXCEPTION
Start Date	Day	01	Default to Study Day 0 (day of first injection procedure) if an event starts in the same year and month as Study Day 0
	Day/Month	01JAN	Default to Study Day 0 if an event starts in the same year as Day 0
Stop Date	Day/Month	Last day of the month	Default to the End of Study Date if the imputed event stop date is after the End of Study Date or before start day of the event
	Day/Month	31DEC	Study Date or before start day of the event

Table 7 Imputation Rules for Partial or Missing Adverse Event Start and Stop Times

	Missing	IMPUTATION	EXCEPTION
Start Time	Minute	00	Default to time of first injection if an event
	Hour: Minute	00:00	starts on Study Day 0
Stop Time	Minute	59	(none)
	Hour: Minute	23:59	Default to 23:59 on the End of Study Date if
			the imputed event stop date is after the End
			of Study Date or before start day of the event

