9.4.4.1. Time to complete wound closure of foot ulcer

The log-rank test will be used to compare the distributions of the time to complete wound closure (event) between the treatment groups. Kaplan-Meier estimates of the survival function for each treatment group will be graphically displayed. Kaplan-Meier estimates of quartiles

Helixmith Co., Ltd.

Page 26 of 31

¹ Gail, MH, and Simon, R., Testing for qualitative interactions between treatment effects and patient subsets. Biometrics, 1985;41: 361-372.

(25th, median, and 75th percentiles) with 2-sided 95% confidence interval will be calculated if estimable.

The log-rank test and Kaplan-Meier methods above will be performed for this endpoint for each subgroup identified in Section 7.5 meeting the minimum group size requirement. Differences between the time-to-event distributions of the treatment groups will be compared adjusting for the subgrouping variable using the log-rank test with the subgrouping variable added as a stratification factor in the modeling.

9.4.4.2. Proportion of subjects with a wound closure by 7 months.

The proportion of subjects with wound closure by the 7-month follow-up will be calculated for each treatment group. The 95% confidence intervals of the proportion will be provided based on the binomial distribution and the exact 95% confidence intervals of the proportion difference will also be obtained. Fisher's exact test will be used to compare the proportions between two treatment groups.

The subgroup analyses described in Section 9.4.2 will also be performed for this exploratory endpoint.

9.4.4.3. Percent change in wound volume at 2, 2.5, 3, 4, and 7 months

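### Time to wound closure: unhealed subjects are censored at an undefined end-of-study date rather than at the last wound assessment, which can lower the closure curves (minor, exploratory endpoint)

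*SAP*

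**What the plan says.** SAP 5.4 counts time to closure from Day 0 to "the date of the first visit date within the allowed visit window where wound closure is so indicated by the investigator". For subjects without closure: "If a subject has not experienced complete wound closure, the subject will be considered censored at the subject's end of study date". The only other use of the term is in the imputation table of SAP 8.6.3, as a cap on adverse event and medication stop dates ("Default to the End of Study Date if the imputed event stop date is after the End of Study Date"); it is not defined there either.

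SAP 9.4.4.1 sets the analysis: "The log-rank test will be used to compare the distributions of the time to complete wound closure (event) between the treatment groups", with Kaplan-Meier curves and quartiles. SAP 9.4.4 places it in the ITT population, which SAP 7.1 defines as everyone randomised. SAP 8.4 gives its standing: "analyses for other efficacy endpoints are exploratory".

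On observation of the wound, SAP 3 has subjects "come to the clinic once a week for dressing changes and wound assessment until the ulcer has healed or study exit". For early leavers, Protocol 3.5.2 says: "Subjects that withdraw after receiving any treatment injections but prior to study completion will undergo the following, if possible", and the list that follows includes ulcer documentation. For those who disappear: "In case of a subject lost-to-follow-up, the investigator/designee must do his/her best to contact the subject (by phone or letter) at least twice", after which relatives or the general practitioner may be approached. No rule fixes the exit date. Protocol 3.4.8.1 gives no early termination visit to subjects who are randomised but leave before dosing. SAP 10 records that the study stopped early.

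**The concern.** The event can be recorded only at a visit, while the censoring date is not tied to one. Any interval between the last look at the wound and the end-of-study date is scored as if the wound had been seen and found open. A subject last seen on Day 35 whose record closes on Day 120 would add 120 - 35 = 85 unobserved days to the risk set.

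Four groups could have such an interval: subjects lost to follow-up, withdrawals with no exit assessment, subjects randomised but never dosed, and subjects given an administrative exit date when the study stopped. Completers have ulcer documentation at Day 210, and leavers who attend the exit visit have it there, so for them the two dates should coincide.

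At stake are the level of the closure curves and the quartiles read from them and, if loss differs between arms, the log-rank comparison.

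**Working it through.** The documents state no figure for time to closure, so there is none to reproduce. The check compares the two censoring rules on the same simulated subjects.

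**Inputs.** From the documents: weekly assessments; 210 days of follow-up; 50% closure by four months, the low end of the SAP section 6 range for VM202. Assumed: exponential healing; 20% of subjects lost, evenly over Days 0-120 and independently of healing; no exit visits; a lag from last visit to end-of-study date of 0, 14, 30, 60 or 90 days, or running to Day 210.

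**Worst case by hand.** The closure function is F(t) = 1 - 2^(-t/120). The last weekly visit before Day 120 is Day 119, so F(119) = 0.497; F(210) = 0.703. If every lost record stays open to Day 210, nobody leaves the risk set early, and the Kaplan-Meier estimate is simply the proportion with a recorded closure. For a lost subject, averaging F over the last attended visit (weight 7/120 for each of Days 0, 7, ..., 112 and 1/120 for Day 119) gives 0.264. Hence:

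- Day 120: 0.80 × 0.497 + 0.20 × 0.264 = 0.450, against 0.497.
- Day 210: 0.80 × 0.703 + 0.20 × 0.264 = 0.615, against 0.703.

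**Shorter lags, by simulation** (400,000 subjects, 20% lost):

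| Lag after last assessment | Closure at Day 120 | Closure at Day 210 |
|---|---|---|
| 0 days | 49.7% | 70.3% |
| 14 days | 48.8% | 69.7% |
| 30 days | 48.0% | 69.1% |
| 60 days | 46.6% | 67.8% |
| 90 days | 45.6% | 66.2% |
| to Day 210 | 45.0% | 61.5% |

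**Between-arm comparison.** A separate simulation used 200 vs 100 subjects, true four-month closure of 50% vs 30%, and independent dropout by Day 210. A positive log hazard ratio favours VM202.

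| Loss VM202 / placebo | Last assessment | 30-day lag | To Day 210 |
|---|---|---|---|
| 20% / 20% | 0.599 | 0.598 | 0.576 |
| 30% / 10% | 0.613 | 0.582 | 0.461 |
| 10% / 30% | 0.593 | 0.620 | 0.696 |

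With equal 20% loss, log-rank power is 0.957, 0.960 and 0.953 in the same order. With no treatment effect (30% closure in both arms) and unequal loss, the two-sided error rate is about 0.04 with last-assessment censoring, 0.04-0.05 with a 30-day lag, and 0.11-0.12 if records close at Day 210.

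**Enrolled size.** SAP section 1 gives 7 + 5 + 16 + 16 = 44 subjects. The split is not stated; 29 vs 15 is assumed. With 40% closure in both arms, loss of 30% vs 10% over Days 0-120 and close-out at Day 210, the error rate goes from 5.6% to 7.6% and the mean log-rank z from about 0 to -0.44.

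**The case against.** The strongest reply is that the gap is inferred. If the database records the last attended visit as the end-of-study date, the two rules are identical. This stands: the text permits the bias but does not establish it. A reader might infer that lost subjects certainly remain at risk unobserved and that healing is therefore understated. The documents do not support that, because the date is undefined and no close-out timing is given. Two contact attempts do not imply a lag of months.

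The 5- and 9-point figures also need every lost subject to have no exit visit and every record to stay open to Day 210. If half of those lost attended an exit visit, a 30-day lag would cost about 0.8 points at Day 120.

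The downward direction is relative to last-assessment censoring, not necessarily to the truth. If non-healers leave more often, last-assessment censoring itself overstates healing. With assumed loss of 12% among subjects who would heal by Day 210 and 35% among those who would not, and a 30-day lag, true Day-120 closure is 49.6%; last-assessment censoring gives 51.9% and the SAP rule 49.9%. That agreement depends on the chosen rates and is no reason to keep an undefined date.

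Finally, precision is poor. At 50% closure, the standard errors are √(0.25/29) = 9 points and √(0.25/15) = 13 points, so a shift of 1 to 2 points could not be discerned. That stands and bears on severity.

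**Conclusion.** The defect is a censoring date that is neither defined nor tied to observation of the wound. It can lower the closure curves relative to last-assessment censoring, but only through unhealed subjects who leave without a final wound assessment, and only if their end-of-study date is later than their last one.

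Under the stated assumptions, the cost at Day 120 is about 1 point for a 14-day lag and 2 points for a 30-day lag. The worst case is about 5 points at Day 120 and 9 at Day 210. It would be tempting to conclude that the treatment comparison is unreliable. The calculations do not show that in general: equal loss leaves it nearly unchanged, unequal loss moves it against the arm with more loss, and material error inflation appeared only with very late close-out.

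Severity is minor. The endpoint is exploratory, and the primary analysis (SAP 9.4.1.1) counts unassessable subjects as non-responders and never uses this date. Confidence is high that the rule is loose and low on the size of any effect, since loss rates and lags are assumptions throughout.

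**What to change.** In SAP 5.4, replace the censoring sentence with: subjects without complete wound closure are censored at the date of their last documented target-wound assessment, whether at a scheduled, weekly, unscheduled or early-withdrawal visit; randomised subjects with no post-baseline assessment are censored at Day 0. Add that the analysis assumes loss is unrelated to healing, and that closure may be overstated if non-healers leave more often.

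The cost is a sentence or two and one derived date. SAP 8.2 already draws on all these visit types for time-to-event endpoints, so no new data are needed. If the two dates prove to coincide, results do not change. If the final analysis has already been run, report the revised version beside it, labelled post hoc.

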1. BACKGROUND

1.1. NONHEALING FOOT ULCERS

Over 6.5 million people in the United States have chronic, nonhealing foot ulcers. 1,2 The ulcers initially occur due to trauma, pressure loading, and / or neuropathy. Ulcers fail to heal and become chronic when the energy demands of wound repair cannot be met because of infection and / or when underlying disease inhibits the normal pathways for energy production.

Chronic wounds are unresponsive to standard therapies and persist despite appropriate care.^{3,4} The majority (approximately 90%) occur in patients with diabetes, but this attribution can be misleading, as 10% - 50% of these patients have concomitant peripheral arterial disease (PAD).⁵⁻¹¹ Most patients have some form of peripheral neuropathy.¹² A small percentage occurs in patients whose primary condition is ischemic, and in whom revascularization / reperfusion has not resulted in wound healing.⁹

The lifetime risk of developing nonhealing foot ulcers for individuals with diabetes is 15 - 25% with a 50% - 70% recurrence rate within 5 years after the index occurrence. 1,2,9,13,14 The chance of developing an ulcer doubles in patients with concomitant PAD. 6,7,9,14 Figure 1 below depicts the chronic foot ulcer population and the degree to which ischemia and diabetes overlap. The area circled by the thick black line characterizes patients with foot ulcers which suffer from both ischemia and diabetes.

[figure not shown]

Figure 1. The overlapping relationship of risk factors associated with developing nonhealing ulcers in the United States^{1,9,11,13,15-17}

Nonhealing ulcers can significantly affect a patient's quality of life, with patients reporting social isolation, unemployment, depression, and feelings of stigma. 18-21

Current treatment strategies result in healing approximately 50% of ulcers, regardless of underlying comorbidity(ies), but most ulcers recur.^{2,22} Twenty-five percent (25%) of open wounds progress to gangrene or enlarge to such an extent that they require amputation. The five-year mortality rate associated with an index occurrence of a nonhealing ulcer is comparable to or greater than that of many cancers.¹⁰ This significant and growing public health concern costs the US healthcare system over \$25 billion annually without accounting for productivity loss.

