Ulcers were evaluated until healed, and, if not healed, to the last available study visit or amputation. If an ulcer was lost due to amputation, the last recorded evaluation of the ulcer was carried forward. Improvement or worsening was determined by changes in ulcer area. The average area at baseline (Day 0) for ulcers in the placebo group was 3.7 cm² (SD 5.6 cm²), 2.7 cm² (SD 6.5 cm²) in the Low Dose group, and 2.9 cm² (SD 4.6 cm²) in the High Dose group. The average increase in wound area was $4.3 \text{ cm}^2 \text{ (SD } 12.6 \text{ cm}^2\text{)}$.

Improvements were statistically significant for wound healing in both treatment groups. Ulcers improved most in the High Dose group when compared to Placebo (p < 0.02). Nine of the 14 ulcers in the High Dose Group (9/14, 64.3%) completely healed. Of the 5 remaining ulcers, 4 improved (4/14, 28.6%) and one worsened (1/14, 7.1%). Improvements were also seen in the Low Dose Group. Fourteen of the 26 ulcers (14/26, 53.8%) present at baseline completely healed. Of the remaining 12 ulcers, 8 improved (8/26, 30.8%), and 4 ulcers worsened (4/26, 15.4%). In the placebo group, only one (1) of the 6 ulcers (16.7%) completely healed from baseline. The 5 other ulcers (5/6, 83.3%) increased in size. Table 3 lists the progression of ulcers at the last available follow-up by treatment group.

Table 3. Progression of ulcers present and documented at baseline by treatment group

TREATMENT	ULCERS PRESENT AT	COMPLETELY HEALED	ULCERS DECREASED IN SIZE, N (%)		ULCERS INCREASED IN SIZE N (%)		
Arm	BASELINE	N (%)	1 - 50%	50 - 99%	1 - 50%	50 - 99%	≥100%
PLACEBO	6	1 (16.7%)	0 (0.0%)	0 (0.0%)	3 (50.0%)	0 (0.0%)	2 (33.3%)
Low Dose (8MG VM202)	26	14 (53.8%)	3 (11.5%)	5 (19.2%)	1 (3.8%)	1 (3.8%)	2 (7.7%)
HIGH DOSE (16 MG VM202)	14	9 (64.3%)	3 (21.4%)	1 (7.1%)	0 (0.0%)	0 (0.0%)	1 (7.1%)

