3.5. STUDY COMPLETION

3.5.1. COMPLETED SUBJECTS

Each subject in the study will be considered completed when all assessments through 7 months have been performed in accordance with the study protocol.

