9.4.4. Other Efficacy Endpoints

All the exploratory efficacy analyses will be based on the available data in the ITT population.

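### Time to wound closure censors deaths, and amputees who leave the study, as if their ulcers could still close, so Kaplan-Meier closure is overstated for those cases (minor, exploratory endpoint)

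*SAP*

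**What the plan says.** SAP Section 5.4 measures time to complete wound closure from Day 0 to the first visit at which the investigator records closure. For all other subjects: "If a subject has not experienced complete wound closure, the subject will be considered censored at the subject's end of study date". The reason follow-up ended plays no part.

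SAP Section 9.4.4.1 uses this variable twice. The first use is a test between arms: "The log-rank test will be used to compare the distributions of the time to complete wound closure (event) between the treatment groups". The second use is descriptive, a curve for each arm: "Kaplan-Meier estimates of the survival function for each treatment group will be graphically displayed". Quartiles with confidence intervals accompany the curves, and the methods are repeated by subgroup. SAP Section 9.4.4 sets the data: "All the exploratory efficacy analyses will be based on the available data in the ITT population". SAP Section 8.4 sets the status: "analyses for other efficacy endpoints are exploratory".

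Neither document mentions a competing event for this endpoint, or says how death or surgical loss of the target ulcer enters it. Major and minor amputations in the target limb are separate time-to-event endpoints (SAP Sections 4.2, 9.4.4.6 and 9.4.4.7) and are not linked to closure.

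On follow-up, Protocol Section 3.5.1 states: "Each subject in the study will be considered completed when all assessments through 7 months have been performed". Protocol Section 3.5.2 allows exit for adverse events. It neither names amputation as a reason to leave nor says that amputees stay.

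**The concern.** Kaplan-Meier censoring assumes that a censored subject would later have closed at the same rate as those still at risk. That cannot be true after death, or after the tissue carrying the ulcer has been removed. The estimator passes that subject's share of probability to the others, and estimated closure rises.

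The rule also treats identical courses differently. An amputee who leaves at Day 60 drops out of the risk set at Day 60. One with the same amputation who attends to Day 210 stays in the denominator as unclosed. The estimate then depends on an exit decision and not on what happened to the ulcer. If these events or exits differ between arms, the curves and quartiles are distorted by different amounts.

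**Working it through.** **The plan's own figures.** The documents give no power, event count or competing-event rate for time to closure, so there is nothing to reproduce for this endpoint. SAP Section 6 supplies only the closure rates assumed by 4 months: 50% to 60% on VM202 and 20% to 30% on placebo. The check uses 25% (middle of the placebo range) and 50% (bottom of the VM202 range).

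**Assumptions.** The proportion who die or lose the target ulcer by amputation by Day 120 is not in the documents; 2%, 5%, 10% and 15% are assumed. Hazards are constant, there is no other dropout, and every such subject leaves at the event. The last assumption makes the results an upper bound. End of study for a death is taken as the date of death.

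**Formulas.** Let Fc be true closure by Day 120 and Fa the competing proportion by Day 120.

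- total hazard: l = -ln(1 - Fc - Fa)/120
- closure hazard: lc = l × Fc/(Fc + Fa)
- true closure (cumulative incidence): CIF(t) = (lc/l)(1 - exp(-l t))
- closure under the SAP rule when cases leave: 1-KM(t) = 1 - exp(-lc t)

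**Example, Fc = 0.50 and Fa = 0.10.** l = -ln(0.40)/120 = 0.007636 per day, and lc = 0.007636 × 0.5/0.6 = 0.006363.

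- Day 120: 1-KM = 1 - exp(-0.7636) = 53.4%, against a true 50.0% (+3.4 points).
- Day 210: 1-KM = 1 - exp(-1.3363) = 73.7%, against CIF = (5/6)(1 - exp(-1.6035)) = 66.6% (+7.1 points).
- Median: ln 2/0.006363 = 109 days by Kaplan-Meier, against 120 days by cumulative incidence.
- Competing events by Day 210: (1/6)(1 - exp(-1.6035)) = 13.3%.

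| True closure, Day 120 | Competing, Day 120 (assumed) | Competing, Day 210 (implied) | Excess of 1-KM, Day 120 | Excess of 1-KM, Day 210 |
|---|---|---|---|---|
| 25% | 2% | 3.1% | 0.3 | 0.7 |
| 25% | 5% | 7.7% | 0.7 | 1.9 |
| 25% | 10% | 15.1% | 1.5 | 3.8 |
| 25% | 15% | 22.2% | 2.3 | 5.9 |
| 50% | 2% | 2.8% | 0.6 | 1.4 |
| 50% | 5% | 6.8% | 1.6 | 3.5 |
| 50% | 10% | 13.3% | 3.4 | 7.1 |
| 50% | 15% | 19.4% | 5.4 | 11.0 |

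Excesses are in percentage points. The largest, 11.0, requires about 19% of subjects to die or lose the ulcer by Day 210, all leaving at once.

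**Cross-check with the competing rate fixed at Day 210.** At 10% by Day 210, the Day 210 excess is 3.0 points for Day 120 closure of 30%, 5.2 for 50% and 6.4 for 60%. Direction and scale agree.

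**Stay or leave at this trial's size.** SAP Section 1 reports 7 + 5 + 16 + 16 = 44 enrolled, so roughly 15 on placebo at 2:1. Take 15 subjects with closures at Days 45, 75, 100, 119, 150 and 180, and amputation of the ulcer at Day 30.

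- Amputees stay to Day 210: the survival product telescopes to 9/15, so 1-KM = 40.0%, equal to the observed 6/15.
- One leaves: 8/14, so 42.9%.
- Two leave: 7/13, so 46.2%.
- Three leave: 6/12, so 50.0%.

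Observed closure is 40% in every case.

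**The case against.** **Is closure always overstated?** A reader might infer that it is. The documents do not support that. Protocol Section 3.2 has all subjects assessed through Day 210, and amputation is not a stated reason to leave. An amputee who stays is handled correctly, so the bias is confined to deaths and to amputees who exit. This limit stands.

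**Are the events common?** A reader might take a rate from Protocol Section 1.1: "Twenty-five percent (25%) of open wounds progress to gangrene or enlarge to such an extent that they require amputation". That figure has no time frame and describes open wounds generally. Protocol Section 3.3.2 excludes patients expected to need amputation or revascularization in the target leg within 3 months, gangrene, active infection, and life expectancy under a year. These point to the lower part of the assumed range, where the excess is about 1 point or less at either time. This stands, although follow-up runs to 7 months and the true rate is unknown.

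**Was a phase II safeguard dropped?** Protocol Section 1.6.4 says: "If an ulcer was lost due to amputation, the last recorded evaluation of the ulcer was carried forward". That served a classification of ulcer size at last follow-up. It was not a time-to-event rule, so its absence here shows nothing.

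**Does the rule contradict the primary analysis?** SAP Section 9.4.1.1 counts subjects not assessable at 4 months as non-responders. That is a binary endpoint, and a time-to-event endpoint may handle exits differently. There is no contradiction. SAP Section 9.4.4.2 also reports closure by 7 months as a proportion, so readers need not rely on 1-KM alone.

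**Must the log-rank test go?** No. With censoring at the competing event it validly compares cause-specific closure hazards. Gray's test answers a different question, because effects on death or amputation enter its result. The narrower difficulty is that the present rule leaves some amputees in the risk set and removes others, so what the test compares is mixed.

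**Does it matter with 44 subjects?** In the example, one departing amputee moves 40.0% to 42.9%, while the standard error of 40% with 15 subjects is √(0.4 × 0.6/15) = 12.6 points. Sampling error dominates. That supports a low severity, but does not justify a rule that gives two answers for one outcome.

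**Conclusion.** The point holds in a conditional form. Followed as written, SAP Section 5.4 overstates Kaplan-Meier closure and shortens its quartiles for deaths and for amputees who leave, but not for amputees who stay to Day 210.

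For true Day 120 closure of 25% to 50%, the upper bound is about 0.3 to 5.4 points at Day 120 and 0.7 to 11.0 points at Day 210. This rests on assumed competing rates of 2% to 15% by Day 120 (about 3% to 22% by Day 210), constant hazards and immediate exit of every case. None of those rates comes from the documents, and eligibility makes the upper end unlikely.

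Severity is minor: the endpoint is exploratory and the primary Fisher test is not affected.

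**What to change.** Before unblinding, amend SAP Sections 5.4 and 9.4.4.1:

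- Define death, and amputation of the part bearing the target ulcer, as competing events for time to closure. An amputation elsewhere on the limb is not one.
- Report the cumulative incidence of closure, with its quartiles, in place of 1-KM. A simpler alternative is to keep these subjects as unclosed to Day 210; without other dropout the two give the same curve.
- Keep the log-rank test, labelled as the cause-specific comparison, with censoring at the competing event. Gray's test is optional.
- State that removal of the ulcer by amputation is not wound closure. The closure definition in SAP Section 5.3.2 does not say so.

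Cost: SAP wording, one additional estimator, and a short blinded check. The amputation review in SAP Section 5.3.2 establishes level and limb side, but not whether the removed part carried the target ulcer. Each target-limb amputation must therefore be compared with the recorded wound location (SAP Section 4.5). Reported closure will be slightly lower wherever such events occurred and the subject left.
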